7.7. Follow-Up Contact (Day 30 ± 3)

Refer to Tables 1 and 3 for schedule of procedures at final inpatient visit. Procedures to be performed by PI and Study Coordinator.

Day 30 Visit

This follow-up visit will occur in-person, on the phone, or over HIPAA-secured Zoom call, depending on the subject's preference.

- **Self-Report Measures:** Electronic versions of the following surveys will be administered: EPDS; STAI (Y1&Y2); SCS; BIMF; IDS-SR; RRS-10; SHAPS.
- **Semi-Structured interview:** Study coordinator or PI will administer the HAM-D
- **Exit Interview:** an informal interview with PI to include items such as:
 - What is your mood like today?
 - Do you feel the same as, worse than, or better than you did when you left the hospital? (If worse than, when did your mood start to decline?)
 - Have you had any trouble with your thinking?

- How stressed do you feel? Have you had any stressful life events since leaving the hospital?
- Do you have any current illnesses?
- How would you describe your experience participating in this research study?
- Do you have any feedback you'd like to share about your experience in this study or with the study drug?

7.8. Premature Discontinuation

If a subject withdraws or the investigator discontinues subject participation, the subject will be offered the optional exit interview session with PI to discuss her experience in the study protocol and assessment conducted while enrolled. Safety assessments will be performed on subjects who withdraw prematurely following initiation of brexanolone and include the following: clinical lab assessments, vital signs, 12-lead ECG, C-SSRS, and evaluation of adverse events.

In the unlikely event that there is imminent risk of suicidal behavior at the time of the final safety check, the subject will be withdrawn from the research study, discharged from the Women's Hospital, and referred to the UNC Emergency Department and/or other appropriate inpatient hospitalization. The study doctor will provide referrals for continued care, which may include hospitalization, but will not be responsible for providing such care following withdrawal from the research study.

7.9. Collection and Management of Tissue Specimens

Sample Preparation:

Not applicable.

Record Keeping and Monitoring:

Record keeping and monitoring will be managed by Study Coordinator using secure, encrypted, and HIPAA-compliant data management system (REDCap) provided by UNC. Data will be recorded in real time and verified by Study Coordinator for accuracy and completion. Study records and data collection will be reviewed in regularly scheduled meetings by Study Coordinator and PI.

Sample Storage and Security:

Experimental samples are not applicable.

8. Study Measurements and Evaluations

See Tables 2-4 for descriptions and schedule of study measurements and evaluations.

8.1. Outcome Measures for Evaluation of Feasibility / Tolerability

1. Number of successfully analyzed EEG recordings.
2. Number of subjects completing the entire study protocol through the follow-up phase.
3. Number of subjects withdrawn from the protocol due to participation burden.

8.2. Outcome Measures for Evaluation of Efficacy

Not applicable

8.3. Outcome Measures for Evaluation of Safety

1. Number of subjects withdrawn from the protocol due to adverse events.

8.4. Other Outcomes in the Causal Pathway

Not applicable

8.5. Baseline Characteristics of the Participants

1. Age
2. Race
3. Ethnicity
4. History of depression (SCID-5)
5. Comorbid anxiety disorder(s) (SCID-5)
6. Concurrent psychotropic medication use
7. Pregnancy history (# pregnancies, # births, methods of delivery, birth complications, past PPD episodes)

8.6. Variables Representing Treatment

Not applicable to feasibility study.

9. Statistical Analysis Plans

9.1. Strategies that Apply to all the Specific Aims

To help ensure replicability of the research, the analysis plans will be reviewed and finalized prior to collection of data (a priori). As this is a feasibility study, descriptive rather than inferential statistics will

be employed. All statistical estimates of population parameters will be tabulated along with corresponding confidence intervals (CI) or standard errors (SE). Where appropriate (i.e., in aggregate measures where we might observe a change from pre to post infusion, such as nodal flexibility, spectral power, and symptom rating scales) means and confidence intervals will be calculated for the differences in means pre and post infusion. Point estimates and CI will be used to inform effect size where appropriate. All missing values and drop-outs will be detailed in the database. Descriptive graphical and tabular methods will be used to characterize the participants, visualize the data, and examine relationships among variables.

9.2. Description of the Study Cohort

Descriptive methods to characterize the study cohort will include use of graphical figures, sample means, sample standard deviations, minimum, maximum, frequencies, and counts. Parameters examined will include age, parity, history of MDD, latency of onset, symptom rating scales (EPDS, HAM-D, anhedonia, rumination, complacency state scale, side effects), race, ethnicity, concurrent meds, concurrent anxiety disorder. For ordinal or ordered metric variables (symptom ratings), we will estimate means and confidence intervals. Mood measures will be used to see if the trajectory of treatment response is monotonic or whether it shows different trajectories by different symptom domains across individuals.

9.3. Aim-Specific Plans

Plans for Aim 1:

To evaluate the feasibility of obtaining serial EEG recordings in women with PPD who receive inpatient BRX infusion treatment. Measures obtained will include (1) the number of successfully completed EEG recordings, with particular interest in the quality of EEG data from hours 4 to 8 (to assess the viability of electrode net for extended time period); (2) the number of subjects who complete the entire study protocol through the 30-day follow-up period; and (3) the number of subjects withdrawn from the protocol due to adverse events and/or participant burden. (Quality of EEG data is determined by visual inspection to identify missing or corrupted signal. An automated process will be used to detect poor electrodes and flag them for interpolation. An infomax independent component analysis (ICA) will be performed to separate plausible neural activity from eye blinks, eye movement, muscle activity, heartbeats, and channel noise.)

Plans for Exploratory Aims:

Exploratory Aim 1: To calculate nodal flexibility at baseline, during, and following BRX infusion. As per the published work of Co-I [name], nodal flexibility is a measure of how often major neural hubs change the networks (communities) in which they participate. We will display, in tabular and graphic form, the nodal flexibility during the affective probe and resting state across time points in each subject, in the group as a whole, and in the groups of those who do and do not respond to BRX. We will calculate and display means and confidence intervals (in tables) and means and standard errors (in graphs). Point

estimates and confidence intervals will be used to inform subsequent calculations of effect sizes (pre vs post differences in nodal flexibility). Despite the small sample size, we are confident that we will be able generate meaningful population estimates, as prior work by [name] and colleagues identified very robust effect sizes in small samples of subjects at risk for schizophrenia vs controls. This study included 6 different conditions (before/after stress by N=0,1,2) with 64 electrodes. Data were time-averaged flexibilities calculated from multilayer modularity community detection on the temporal network of electrodes defined by theta band correlations over 3 second intervals. Estimating effect size with Cohen's d with the combined $s = \sqrt{s_1^2 + s_2^2}$ of whole-brain flexibility (which averages overall electrodes equally) yielded d for each of the 6 tests individually ranging from 0.8 to 1.2. Further, with concatenated data, a support vector machine (SVM) supervised classification method successfully separated the two subject groups with accuracy 91.2% +/- 9.8%.

Exploratory Aim 2: To characterize rapid brain state configurations (global brain states) and their probability density function at baseline, during, and following the BRX infusion. Brain states will be determined with two assessment methods. 1) Microstate analysis generates four canonical patterns of correlative voltage distribution. Parameters generated include the duration of each microstate (which we will examine) and the sequence of its occurrence (which we will not examine in this pilot). We will calculate, and display in a table, means and confidence intervals for the duration of each microstate during the affective probe and resting state across time points in the group as a whole and in the groups of those who do and do not respond to BRX. 2) AMICA is an unsupervised means of decomposing EEG signals to generate recurring, quasi-stable patterns of correlated voltage distribution (global brain state). The EEG signal is divided into time windows (one second), each of which serves as a correlation matrix. The matrices are decomposed with independent component analysis to yield brain states that account for much of the variance in the EEG signal, and the probability of appearance of the models generated is then displayed as a probability density function (PDF). We will first create this template, and then graphically display the template PDF for each EEG session.

Exploratory Aim 3: To assess the ability of the iMotions Affectiva software to identify differences in affective state (determined by symptom ratings). Our previous data demonstrate delayed self-recognition of change in affective state, which suggests that affect state changes occur and manifest (to others) prior to a subject's labeling (and recognizing) the state change as having occurred. Affectiva is a software that permits detection of emotion in facial expression by examining and integrating key alterations in facial musculature. The software calculates emotion scores, or the percent time spent in a certain affective state, as the weighted average of action units (tiny musculature changes). We will display in tabular form the emotion scores during the affective probe in each session across all five time points and will plot the percentage of time spent in each affective state against the HAM-D ratings and responses to the semi-structured interview.

Exploratory Aim 4: To assess the amplitude of left frontal midline theta oscillations by performing spectral analyses of data collected from five serial EEG recordings. Fast Fourier transform will be applied to each two-second EEG epoch, and the average spectral power will be calculated within the canonical theta frequency band from 4 to 7 Hz. To estimate frontal midline theta (FMT), theta power in electrode FCz will be log-transformed and then normalized for each participant using the z-transformation across the 90 scalp data channels. Point estimates and CI will be presented in tabular form.

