iMotion Affectiva Facial Expression Analysis Software	Baseline, during infusion (Hours 4, 8, and 28), 12 hours post-infusion	Software that measures 20 facial expression metrics (e.g., affective valence, engagement, facial landmarks) known to display altered configurations that map onto emotions. Changes in facial expression will provide a non-verbal complement to self-ratings in detecting BRX-induced alterations in affective state.	See Table 1C for description of iMotions software outcomes of interest.
Semi-structured Interview	Baseline, during infusion (Hours 4, 8, and 28), 12 hours post-infusion	Administered simultaneously with iMotions recording to elicit emotional response	Qualitative responses to questions about recent experiences

		in lieu of an affective probe task	of enjoyment, guilt, and irritability will be compared to software output of detected facial expression (see Table 1C).
--	--	------------------------------------	---

Table 1B: EEG Outcomes of Interest (Exploratory Aims)

Exploratory Aim	Variable of Interest	Brief Description of Measurement
Calculation of resting state nodal flexibility (community detection)	Nodal flexibility: Frequency with which a nodal hub changes its community identity	Measured by allegiance of nodes to modules: the number of times that each node changes module allegiance normalized by the total possible number of changes. The flexibility of the network as a whole is equal to the mean flexibility over all the nodes
Identification of (A) rapid state brain configurations (global brain states) and (B) their probability density function	(A) Microstate: four quasi-stable, recurring topographic patterns of voltage (i.e., different configurations of electric field lasting 80-120 milliseconds). (B) Duration: frequency of occurrence of microstates reflects the tendency of its underlying neural sources to become activated	Frequency = the number of times a microstate is present relative to the total number of microstates recorded. Average duration = average time in milliseconds. Duration = proportion of time that state is activated relative to the sampling recording.
Calculation of amplitude of frontal midline theta oscillations (spectral analysis)	Frontal Midline Theta: 4-7 Hz reflecting activity from the limbic system and hippocampal regions	Extracted theta power (4-7Hz) from FCz electrode during resting state recordings. Unit = dB.

Table 1C: iMotions Affectiva Software Outcomes of Interest (Exploratory)

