7.3. Enrollment / Baseline (Day 0)

Refer to Tables 1 and 3 for schedule of procedures at Baseline. Procedures to be performed by the following personnel: PI, Study Coordinator, Research Nurse, and/or EEG technician.

Baseline (Hour 0)

- Subject will be admitted to UNC Hospital on a Monday or Tuesday morning. Prior to administration of drug intervention, the subject will undergo the following procedures:
 - Measure subject's height and weight, record, and submit to IDS to calculate drug dosage
 - Negative drug/alcohol and pregnancy test (if positive, subject will be withdrawn from the study)
 - Baseline blood sample to measure circulating allopregnanolone levels
 - Vital signs
 - Review of current concomitant medications and nonpharmacological interventions
- **First EEG recording:**

- EEG cap will be fitted by technician and electrodes filled with gel solution. Impedance will be measured to ensure proper adherence to scalp. Cap set-up will take approximately 20 minutes.
- Recording of 8-minute resting state EEG, eyes alternating open and closed at regular intervals.
- Cap will remain on the subject until the end of the Hour 8 session, so as not to disrupt the electrode placement over the course of the serial recordings. EEG will be recorded for 8-minute sessions at Hours 4 and 8 on Day 1 (not continuously throughout the day).
- **Self-Report measures:** Electronic versions of the following surveys will be administered: C-SSRS, EPDS; STAI (Y1&Y2); SCS; BIMF; IDS-SR; RRS-10; SHAPS.
- **Semi-Structured interview & iMotions Recording:** Facing a laptop equipped with a standard camera and microphone and iMotions Affectiva software, the subject will be administered a semi-structured interview about depressive symptoms and affect by study personnel. Interview questions will include the HAM-D and additional questions to assess the subject's experiences of enjoyment, guilt, and irritability. The interview and recording will last 10-20 minutes. A memory probe task will be completed, in which a subject will be asked to think of a sad event in her life and focus on that memory for 30 seconds while the laptop camera records her facial expressions. Then they will be asked to rate their emotional experience during that recall. This procedure will be repeated with a prompt to recall a happy memory from her life. Subjects will then be asked to come up with a word or phrase that can be used to recall each event during later recording sessions.

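### Exploratory Aim 3 plans no comparison of the facial-expression scores with the cued sad/happy recall or with the women's own recall ratings, although both are collected at all five sessions

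*Combined protocol and SAP*

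**What the plan says.** Section 9.3, Exploratory Aim 3, takes symptom ratings as the definition of affective state and plans two outputs. The first is a table: "We will display in tabular form the emotion scores during the affective probe in each session across all five time points". The second is to "plot the percentage of time spent in each affective state against the HAM-D ratings and responses to the semi-structured interview". Table 1 in Section 4.3 repeats the interview comparison, naming enjoyment, guilt and irritability. It also describes the interview as used "in lieu of an affective probe task".

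The visit sections nevertheless include a memory probe task. At baseline (Section 7.3) the woman recalls a sad event for 30 seconds on camera. "Then they will be asked to rate their emotional experience during that recall". The same steps, filming and rating included, are then gone through for a happy event. Sections 7.4 and 7.6 repeat the sad and happy recalls, cued by a word or phrase, with filming and rating, at Hours 4, 8, 28 and 72.

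Section 9.1 makes all analyses descriptive and says the plans will be finalised before data collection.

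**The concern.** The recalls are the only recordings with an assigned valence and a rating tied to that footage. They offer a direct check: does the software score the happy recall differently from the sad one, and do its scores follow what the woman says she felt? Section 9.3 does not ask either question.

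What it does plan runs mainly across sessions. Every woman receives the infusion, so session number, elapsed hour, infusion rate, repetition of the same cue and clinical course are tied together. A score that drifts for any of these reasons can line up with falling symptom ratings without registering emotion. Section 9.3 adds a further ambiguity. It expects affect to change visibly before the woman recognises the change, so poor agreement could mean either software failure or early detection.

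At stake is whether Aim 3 gives an interpretable answer.

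**Working it through.** Aim 3 states no figure to reproduce. The check sets what is collected beside what is analysed, then counts the data and looks at what each comparison can show.

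**1. Collected versus analysed**

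| Item | Collected | Analysis in Section 9.3, Aim 3 |
|---|---|---|
| Sad and happy recall footage | 7.3, 7.4, 7.6: five sessions | Possibly the affective probe table; no split by cue stated |
| Woman's rating of the recall | 7.3, 7.4, 7.6: five sessions | None |
| Interview on enjoyment, guilt, irritability | 4.3, 7.3, 7.4, 7.6 | Plotted against percent time in state |
| HAM-D | Full at Hours 0, 28 and 72; modified at Hours 4 and 8 (7.3, 7.4, 7.6) | Plotted against percent time in state |

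The full HAM-D therefore accompanies three of the five recording sessions. The five points on that plot are not on one scale unless it is restricted to the shared items.

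**2. Amount of data**

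- 12 women × 5 sessions × 2 recalls = 120 clips, or 60 sad-happy pairs.
- 10 completers × 5 sessions × 2 recalls = 100 clips, or 50 pairs.

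**3. What each comparison can show**

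Write a woman's score at session t as a + d(t) + emotion signal + noise, where a is her own level and d(t) is drift unrelated to emotion.

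- Across sessions, d(t) stays in the score. If symptom ratings also move with t, the two correlate even when the emotion signal is zero.
- Within a session, happy minus sad = (a + d(t) + signal for happy) − (a + d(t) + signal for sad) + noise. Both a and d(t) drop out. Drift that flattens all expression, such as drowsiness, can shrink the difference but cannot create one.

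**4. Illustration of the shared trend (all inputs assumed; none is in the documents)**

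Inputs: 12 women, HAM-D falling linearly from 28 to 9 over 72 hours, HAM-D SD 3 between and 2 within women, score SD 0.7 between and 0.7 within, no software validity, 4,000 simulated trials.

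| Drift over five sessions | Mean pooled correlation, drift linear by session | Mean pooled correlation, drift linear by hour |
|---|---|---|
| 0 | 0.00 | 0.00 |
| 1 SD | −0.28 (5th to 95th percentile −0.46 to −0.09) | −0.33 |
| 1.5 SD | −0.39 | −0.45 |

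Centring both variables within each woman does not help: at 1 SD drift by session the mean correlation becomes −0.42, because centring removes between-woman noise and leaves the trend.

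**5. Precision of the added check (also assumed)**

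Suppose 80% of 50 pairs come out in the expected order. With effective n = 50 / (1 + 4 × ICC), the exact 95% interval is:

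- ICC 0 (effective n 50): 0.66 to 0.90
- ICC 0.5 (effective n 16.7): 0.54 to 0.95
- ICC 1 (effective n 10): 0.44 to 0.97

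The interval must allow for clustering by woman; treating 50 pairs as independent would overstate precision.

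**The case against.** Several stronger readings are tempting, and the documents do not support them.

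- *The HAM-D is the only comparator.* It is not. Section 9.3 and Table 1 both add the interview answers, which are specific to emotions, and the State Complacency Scale also collects self-rated mood, anxiety and irritability. None of these is tied to a recall clip with an assigned valence.
- *The recall clips are unused.* The affective probe in the table may well be the memory probe task. What is clearly unused is the sad/happy contrast and the ratings.
- *Pooling sad and happy clips cancels the signal.* Section 9.3 does not say they are pooled. The planned emotion scores are percent time in separate emotions (Table 1C lists seven), so pooling would dilute them. Only a single positive-to-negative valence score could cancel.
- *The contrast should become the main Aim 3 result.* Aim 3 defines affective state by symptom ratings, and Table 1 speaks of changes brought about by the drug. A within-session contrast holds that state roughly fixed, so it cannot answer the stated question alone. The plan's own remark on delayed self-recognition is also a reason not to rest the aim on self-rating.

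The contrast has limits of its own. At baseline the sad recall comes first, so order and carry-over can enter, and a happy cue does not guarantee happy affect in a depressed woman. The simulation depends wholly on assumed drift and is zero without it. Section 2.1 describes response within 8 to 24 hours, which a linear fall over 72 hours does not match. The plan also specifies a plot, not a correlation.

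All of this stands, and it limits the point to an omission and an undefined term. It does not supply the missing comparison or remove the time trend from the planned plots.

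**Conclusion.** The point holds as a minor one. Aim 3 leaves its affective probe undefined and plans no comparison with the cued sad/happy condition or the recall ratings, for up to 60 pairs (50 with 10 completers). As written, the HAM-D and interview plots are weak evidence of software validity: there is no untreated comparison to separate validity from a shared time trend, and the HAM-D changes form at two of the five sessions. These conclusions rest on the text alone. How far a trend could mislead is not known from the documents; under the assumptions above, the mean correlation with no validity runs from 0.00 without drift to −0.45 at 1.5 SD. The aim is exploratory and descriptive, and the primary outcomes in Section 4.4 are unaffected.

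**What to change.** In Section 9.3, Exploratory Aim 3:

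1. Define affective probe. If the memory probe task is meant, say so, and reconcile this with Table 1, which says the interview takes the place of a probe task. Exploratory Aims 1 and 2 use the same term and need the same definition.
2. Tabulate emotion scores separately for sad and happy recall at each session.
3. Report the within-session happy-minus-sad difference descriptively, with an interval obtained by resampling women rather than clips.
4. Plot the scores against the woman's own recall rating, and name the scale of that rating, which the visit sections do not give.
5. Keep the HAM-D and interview plots, and present items 2 to 4 as a supplementary check beside them. Add a caveat that agreement across sessions may reflect a common time trend. State how the modified HAM-D at Hours 4 and 8 is handled. Redrawing the HAM-D as within-woman change does not remove drift.
6. Note the fixed sad-then-happy order at baseline, and that the cue is not proof of the emotion felt.

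The cost is SAP wording, one more table and one more plot. No new data are needed.

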4.4. Outcome Measures

Primary Outcome(s):

1. Number of successfully analyzed EEG recordings.
2. Number of subjects completing the entire study protocol through the follow-up phase.
3. Number of subjects withdrawn from the protocol due to adverse events and/or participation burden.

Tertiary/Exploratory Outcome(s):

1. Calculation of resting state nodal flexibility (community detection) at H0, 4, 8, 28, 72.
2. Identification of (A) rapid state brain configurations (global brain states) and (B) their probability density function at H0, 4, 8, 28, 72.
3. Identification of affective states with iMotion Affectiva software at H0, 4, 8, 28, 72.
4. Calculation of amplitude of frontal midline theta oscillations (spectral analysis) at H0, 4, 8, 28, 72.

Other Measures: Baseline Characteristics

1. Age
2. Race
3. Ethnicity
4. History of depression (SCID-5)
5. Comorbid anxiety disorder(s) (SCID-5)

6. Concurrent psychotropic medication use
7. Pregnancy history (# pregnancies, # births, methods of delivery, birth complications, past PPD episodes)

5. Study Participants

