7.4. Study Visits (Days 1-4)

Refer to Tables 1 and 3 for schedule of procedures at study visits following Baseline. Procedures to be performed by the following personnel: PI, Study Coordinator, Research Nurse, and/or EEG technician.

Hour 4 Visit

- **Second EEG recording:** With the cap in place from the baseline recording, electrode impedance will be measured, and electrode gel refilled to ensure proper fit. A second EEG will be recorded during an 8-minute resting state with eyes opened and closed at regular intervals. The cap will remain on the subject until the end of the Hour 8 recording but will not be recording continuously between sessions.
- **Self-Report measures:** Electronic versions of the following surveys will be administered: SMDDS, EPDS, STAI (Y1), and SCS.

- **Semi-Structure interview & iMotions Recording:** Facing a laptop equipped with a standard camera and microphone and iMotions Affectiva software, the subject will be administered a semi-structured interview about depressive symptoms and affect by study personnel. Interview questions will include a modified version of the HAM-D (items suitable for repeated measure within the same day) and additional questions to assess the subject's experiences of enjoyment, guilt, and irritability. The interview and recording will last 10-20 minutes. The memory probe task will be completed, in which a subject will be told the predetermined word or phrase to cue recall of the sad and happy events, while the camera records her facial expressions for 30 seconds for each event and the subject rates her emotional experience.

Hour 8 Visit

- **Third EEG recording:** With the cap in place from the Hour 4 recording, electrode impedance will be measured, and electrode gel refilled to ensure proper fit. A third EEG will be recorded during an 8-minute resting state with eyes opened and closed at regular intervals. Following completion of this recording, the cap will be removed.
- **Self-Report measures:** Electronic versions of the following surveys will be administered: SMDDDS, EPDS, STAI (Y1), and SCS.

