9.5. Plans for Coping with Withdrawals and Loss-To-Follow-Up

Given that these are hospitalized inpatients, we anticipate that no more than 20% (two subjects) will fail to complete the study through the inpatient phase (5 EEG sessions). As such, we will recruit 12 subjects in order to obtain 10 completers. In the event that subject discontinuation exceeds our expected limits, we will calculate and display point estimates for as many sessions as the subject completes. Similarly, in the event of unusable EEG data, we will calculate and display point estimates for those sessions with reliable EEG readings.

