9.6. Sample Size Rationale

The choice of sample size was based on expert opinion, availability of subjects, and funding limit; we predict that 10 participants may be sufficient for two purposes: 1) to determine the feasibility of obtaining multiple, high quality EEGs during a BRX infusion; and 2) to provide adequate precision for the estimators of variance components and other parameters for which information is needed to plan a future study. With a conservative expected drop-out rate of 20%, we will enroll 12 subjects to attain 10 completers.

10. Safety Monitoring and Management

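### Exploratory Aim 4: Table 1B defines FCz theta power in dB, but section 9.3 estimates a z-score across channels, which on its natural reading cannot show a rise common to the whole scalp

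*Combined protocol and SAP*

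**What the plan says.** **The variable.** Table 1B (section 4.3) describes frontal midline theta as "Extracted theta power (4-7Hz) from FCz electrode during resting state recordings. Unit = dB". The exploratory outcome list in section 4.4 reads "Calculation of amplitude of frontal midline theta oscillations (spectral analysis) at H0, 4, 8, 28, 72". The aim itself, as restated in section 9.3, is "To assess the amplitude of left frontal midline theta oscillations by performing spectral analyses".

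**The estimator.** Section 9.3 then says that "theta power in electrode FCz will be log-transformed and then normalized for each participant using the z-transformation across the 90 scalp data channels", and that point estimates with CIs will be tabulated. It fixes the electrode, the channel set and the participant level. It names neither the reported scale nor the recordings that supply the mean and SD.

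**The contrast.** For aggregate measures, section 9.1 says "such as nodal flexibility, spectral power, and symptom rating scales) means and confidence intervals will be calculated for the differences in means" before and after infusion. Spectral power is on that list, again without a scale. Section 9.6 gives as one purpose of the sample size "to provide adequate precision for the estimators of variance components and other parameters for which information is needed to plan a future study".

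**Separate point, probe EEG.** Under Exploratory Aims 1 and 2, section 9.3 promises nodal flexibility and microstate duration for an affective probe as well as for rest. Footnote j of Table 3 places the iMotions recording within the EEG recording. Sections 7.3 to 7.6 describe only an 8-minute resting EEG at each session, with the cap taken off after it at H8, H28 and H72. They put the memory probe under the iMotions item, as a camera recording. Table 1 says an interview replaces an affective probe.

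**The concern.** Decibels of FCz power and a z-score across channels answer different questions. The first asks whether theta at FCz rose. The second asks whether FCz rose relative to the other electrodes. Section 2.2 hypothesizes an increase in frontal midline theta with remission, which is a statement about amplitude. If theta rises broadly across the scalp, a z-score formed within each recording removes that rise by construction, and a table of z-scores would show nothing.

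The stake is limited but concrete. If only the z-score is tabulated, the variable of Table 1B is not reported, and a future study would have no mean change or variance on the dB scale from which to plan.

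The probe wording is a smaller matter: section 9.3 promises EEG summaries for a condition in which the visit sections describe no EEG.

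**Working it through.** The plan gives no numerical figure to reproduce here, so the check is algebra on the two scales.

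**Inputs.** From section 9.3: 90 channels and log power at FCz. Assumed, because the documents give neither: rises of 0.25 to 2, in units of the between-channel SD of log power, and FCz either a typical channel or 1 or 2 SD above the other channels. No dB value for that SD is needed.

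**Set-up.** Scale the other 89 channels to mean 0 and SD 1, and let FCz sit at *a*. The 90-channel mean is *a*/90, so FCz deviates from it by 89*a*/90. The 90-channel variance is [88 + (89/90)*a*²]/89. Hence

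z(*a*) = (89*a*/90) / √{[88 + (89/90)*a*²]/89}.

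**Case 1: all channels rise by r.** FCz and the mean both rise by r and the SD does not change. The change in z is [(x + r) − (m + r)]/s − (x − m)/s = 0, exactly, for any r.

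**Case 2: only FCz rises by r.** The share kept is [z(*a* + r) − z(*a*)]/r. For example:
- *a* = 1, r = 1: z(1) = 0.989 and z(2) = 1.946, so the share is 0.957.
- *a* = 2, r = 2: z(2) = 1.946 and z(4) = 3.662, so the share is 1.717/2 = 0.858.

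| FCz position | r = 0.25 | r = 0.5 | r = 1 | r = 2 |
|---|---|---|---|---|
| typical channel (average over random positions) | 0.978 | 0.977 | 0.973 | 0.958 |
| +1 SD | 0.974 | 0.969 | 0.957 | 0.927 |
| +2 SD | 0.923 | 0.915 | 0.897 | 0.858 |

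The range is therefore about 0.86 to 0.98.

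**Case 3: every channel except FCz rises by r.** This is Case 2 with FCz moving down relative to the rest. With *a* = 1 and r = 1, z goes from z(1) = 0.989 to z(0) = 0, a fall of 0.99, although FCz power has not changed.

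**Case 4: FCz and some other channels rise.** The mean rises, which shrinks the numerator. The SD may grow or shrink. If the sharing channels were already the strongest, the spread widens and the z change is attenuated. If they were the weakest, the spread narrows and the z change can exceed the rise itself. No share can be given without the topography.

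**Probe EEG, side by side.** Section 9.3 (Aims 1 and 2) and Table 3 footnote j point to EEG beyond rest. Sections 7.3 to 7.6 and Table 1 point to resting EEG only. The interview and iMotions recording last 10 to 20 minutes against an 8-minute EEG, so footnote j does not fit the visit text as written. The cap does stay on between H0 and H8, so it is worn through the H0 and H4 interviews. The passages disagree, and neither set overrides the other.

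**The case against.** A channel-wise z is a defensible scale. Section 7.4 says that at H4 and H8 "electrode impedance will be measured, and electrode gel refilled to ensure proper fit", and the cap is re-fitted at H28 and H72. Absolute power is exposed to all of that, and a relative measure less so. Log power is also the natural intermediate for dB, Table 1B is only a brief description, and section 4.4 says amplitude without a unit. Section 9.1 provides for the analysis plans to be finalized before data collection, which leaves room to settle the detail. All of this stands as an argument for keeping the z-score. It does not remove the mismatch, because no passage says that the dB value will be reported.

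Three stronger readings are tempting and not supported.

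- A reader might infer that section 9.3 leaves open a choice that decides whether a change is seen. Pooling over a participant's five recordings would keep 1/√(1 + r²p(1 − p)) of a common rise, where p is the fraction of recordings showing it. For r = 1 this is 0.928 at p = 1/5 and 0.898 at p = 2/5. An H0 reference would keep all of it. But no passage points to pooling or to an H0 reference, and normalizing across channels reads most naturally as within a recording. Section 9.5 does not help either. It says "we will calculate and display point estimates for those sessions with reliable EEG readings" and sets no minimum number of recordings.
- A reader might infer that a shared rise is always attenuated. Case 4 shows that it is not.
- A reader might infer that no probe EEG will exist, or that Aim 3 is undermined. Footnote j prevents the first conclusion. For Aim 3 only the label differs, because facial video is recorded during the memory probe.

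**Conclusion.** The point holds as a mismatch between the defined variable and its planned estimator. Case 1 is exact and needs only the per-recording reading. The 0.86 to 0.98 for an FCz-only rise also rests on the assumed FCz positions and on rises of 0.25 to 2 between-channel SDs. For a partly shared rise, the documents support neither a figure nor a direction.

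The harm is conditional on the z-score being the only scale reported. Aim 4 is exploratory and descriptive, and the primary feasibility outcomes and the sample size are untouched. It is worth correcting because the correction is cheap, not because the study depends on it. The probe-EEG conflict is genuine but minor, and it calls for reconciliation rather than a presumption about which passage is right.

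**What to change.** **Aim 4, section 9.3.** Report the within-subject change in FCz log theta power in dB, from H0 to H72 and also at H4, H8 and H28, with its CI. Show the z-score beside it, labelled as a relative (topographic) measure. State that the z mean and SD come from the same recording, or name the recordings that supply them. Neither scale need be ranked first.

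**Cost.** A sentence or two and one extra table. FCz log power is already computed before the z step, and no new recording is needed. The downside is that dB is more sensitive to impedance, gel refilling and cap re-fitting, which is the reason to show both.

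**Probe EEG, separately.** Reconcile section 9.3 (Aims 1 and 2), Table 3 footnote j, Table 1 and sections 7.3 to 7.6. Either limit the EEG summaries of Aims 1 and 2 to rest and correct footnote j, or describe the probe EEG in sections 7.3 to 7.6. The first is wording only. The second would also require the visit text on cap removal to agree. For Aim 3, use one name for the task throughout.
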